6.3 Dose Adjustments

Dose adjustments for both DFP and DFX will be allowed for efficacy reasons (scaling up) or for safety reasons including the presence of markers indicative of over-chelation (scaling down).

DFP can be scaled up in steps of 12.5 mg/kg/day (to a maximum daily dose of 100 mg/kg) according to the individual patient's response defined as an increase of serum ferritin levels > 20% compared to the previous determination.

DFX will be scaled up in steps of 5 to 10 mg/kg (to a maximum daily dose of 40 mg/kg) according to the individual patient's response defined as an increase of ferritin levels > 20% compared to the previous determination.

For patients with a stable serum ferritin value >1500 (no increase or any increase <20%) and not showing a downtrend over a 3-month-period , DFP or DFX can be also increased.

DFP and DFX must be scaled down for the safety reasons detailed in **Table 4**.

Table 4. Scale down adjustment for DFP and DFX (safety reasons)

Serum creatinine increased by >33% from baseline OR Reduction in creatinine clearance (estimated with the Schwartz formula) ≤ 90ml/min and >60 ml/min in two consecutive measurements	No dose adjustment.	Reduce DFX in steps of 10 mg/kg/day until value returns to baseline value and continue DFX with the adjusted dose for 1 month. If the increase persists interrupt DFX. If after DFX interruption value returns to baseline value or > 90 ml/min for creatinine clearance restart DFX at 50% of the last dose and then escalate by 10 mg/kg/day at 1 month intervals provided that value increase does not recur. Monitor serum creatinine, creatinine clearance and urine protein/creatinine ratio weekly (+/- 7 days) during the period of abnormal value and during the first month after dose modification, then monthly.
Urine protein/creatinine ratio ≥ 0.5 in two consecutive measurements	No dose adjustment.	Reduce DFX in steps of 10 mg/kg/day until value returns to < 0.5. If the increase persists interrupt DFX. After the ratio improves, restart DFX at 50% of the last dose and then escalate by 10 mg/kg/day at 1 month intervals provided that value increase does not recur. Monitor serum creatinine, creatinine clearance and urine protein/creatinine ratio weekly (+/- 7 days) during the period of abnormal value and during the first month after dose modification, then monthly.

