Serum ferritin will be tested in terms of quantitative variable as part of the composite endpoint measurable in the entire experimental population. The purpose of this analysis is to clarify the interpretation of the primary composite endpoint and hence no adjustment for multiplicity will be considered. The population for this analysis is the PP2. ITT analysis will be used to corroborate the findings.

Non inferiority of DFP to DFX will be tested considering a non inferiority margin of 400 ng/mL.

Non-inferiority will be assessed based on the two sided 95% confidence interval $[\delta_L, \delta_U]$ of the difference $\delta = m_1 - m_2$, being m_1 and m_2 the mean difference between baseline and end of treatment assessments of DFP and DFX, respectively, and n_1 and n_2 the numbers of patients randomised to DFP and DFX arms. Non-inferiority will be claimed if δ_L is greater than -400 ng/ml.

The two sided 95% confidence interval for δ will be estimated as follows:

$$(m_1 - m_2) \pm Z_{1-\alpha/2} \sigma \sqrt{\frac{1}{n_1} + \frac{1}{n_2}}$$

where Z_γ is the γ^{th} percentile of the standardised normal distribution and σ^2 is the pooled variance.

Serum ferritin trends over the 1 year period of treatment will be also investigated. A repeated measures analysis of variance model with treatment-group as main effect will be fitted. The H_0 of equal between group regression slopes will be tested by evaluating whether the interaction between the categorical factor (treatment group) and the repeated measure (monthly measures of serum ferritins) equals zero, i.e. no interaction. The rejection of the null hypothesis on the interaction term (treatment group*monthly ferritin measure) will be supportive of different trends between DFP and DFX arms. The ITT population will be used for this analysis. Handling of missing data for this analysis is described in Section 11.4.

Descriptive statistics for trends in subgroups of patients according to age classes will be also provided.

Efficacy measured through cardiac T2* MRI

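### The ferritin trend analysis states a null of equal slopes, but the repeated-measures ANOVA interaction it names conventionally tests parallel visit profiles

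*Combined protocol and SAP*

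**What the plan says.** Section 4.4.1 announces a comparison of ferritin trends over time between the arms. Section 11.6 gives the method in four statements:

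- Model: "A repeated measures analysis of variance model with treatment-group as main effect will be fitted".
- Null and test, in one sentence that begins: "The H_0 of equal between group regression slopes will be tested by evaluating whether the interaction between the categorical factor (treatment group) and the repeated". It ends by asking whether that interaction is zero.
- Conclusion: "The rejection of the null hypothesis on the interaction term (treatment group*monthly ferritin measure) will be supportive of different trends between DFP and DFX arms".
- Population: "The ITT population will be used for this analysis".

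The plan does not say whether time is a factor or a continuous variable. It names no covariance structure or sphericity correction, and gives no alpha or power for this test. Linear mixed models appear only in section 11.13, as a way to impute missing values.

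**The concern.** Equality of two regression slopes is a single constraint. In a conventional repeated-measures ANOVA the occasions are levels of a within-patient factor and no slope is fitted. The interaction then tests whether the difference between arms is the same at every visit. Two arms can have equal linear slopes and still fail that condition. Read literally, the term written in section 11.6 crosses treatment with the ferritin response itself, which does not define a model.

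Curved, arm-specific profiles are plausible here because dose follows ferritin. Section 6.3 ties deferasirox steps to ferritin ("DFX will be scaled up in steps of 5 to 10 mg/kg (to a maximum daily dose of 40 mg/kg) according to the individual patient's"), while deferiprone moves in steps of 12.5 mg/kg/day.

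At stake is whether this analysis answers its own stated question. A rejection could be taken as a difference in annual rate when the slopes are equal, a real slope difference could be missed, and no slope difference is estimated.

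**Working it through.** **Inputs from the documents.** 194 per arm randomised and 310 evaluable, so 155 per arm (sections 4 and 11.12). SD of ferritin differences 1000 ng/mL (section 11.12). Monthly values V3–V15 give 13 time points; central values at V3, V6, V9, V12 and V15 give 5 (section 7.3.12).

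**Assumptions not in the documents.** Two-sided alpha 0.05, complete data, the shape and size of the difference between arms, and the share r of the 12-month change variance that is due to patient-specific slopes (0, 0.5 or 0.9; r = 0 is compound symmetry).

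**1. The plan's nearest figure.** The trend test has no stated power. For the separate 400 ng/mL ferritin non-inferiority test, power = Φ(400/(1000·√(2/155)) − 1.96) = Φ(3.52 − 1.96) = 94.1%, which agrees with the stated minimum of 90%.

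**2. The two nulls.** Let d(t) be the difference in arm means at time t.

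- Equal slopes: Σ(t − t̄)d(t) = 0, which is 1 df.
- Parallel profiles: d(t) constant, which is 13 − 1 = 12 df monthly or 5 − 1 = 4 df quarterly.

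The second implies the first, but not the reverse. For example, d(t) = A[1 − ((t − 6)/6)²] is zero at months 0 and 12, equals A at month 6, and has zero linear slope by symmetry.

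**3. Analytic power for a linear difference.** Take slope variance v = r·10⁶/144 per month², residual variance s² = (1 − r)·10⁶/2, S = Σ(t − t̄)² = 182 (monthly) or 90 (quarterly), and β = 200/12 = 16.67 ng/mL per month. Then λ = β²/[(2/194)(v + s²/S)].

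- Monthly, r = 0: λ = 277.8/[(2/194)(500,000/182)] = 9.81. Power is 87.9% on 1 df and 49.5% for the 12-df multivariate test.
- Monthly, r = 0.5: λ = 5.56. Power is 65.5% and 27.4%.
- Monthly, r = 0.9: λ = 4.13. Power is 52.9% and 20.4%.
- At the λ that gives 80% on 1 df, (1.960 + 0.842)² = 7.85, power is 59.5% on 4 df and 39.4% on 12 df.

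**4. Simulation.** 194 per arm, 4000 runs, monthly values, percentage of runs rejecting. GG is the Greenhouse-Geisser-corrected F. The hump is d(t) above with A = 200, the linear difference reaches 200 at month 12, and the early plateau is 200(1 − e^(−t/2)).

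| Scenario | r | F uncorrected | F, GG | Multivariate | 1-df slope |
|---|---|---|---|---|---|
| No difference | 0 | 5.2 | 5.0 | 5.1 | 5.2 |
| | 0.5 | 7.5 | 5.4 | 4.9 | 5.3 |
| | 0.9 | 14.6 | 5.2 | 4.6 | 5.2 |
| Hump, equal slopes | 0 | 59.3 | 58.4 | 58.0 | 4.6 |
| | 0.5 | 86.7 | 81.9 | 91.9 | 5.8 |
| | 0.9 | 100 | 95.2 | 100 | 5.8 |
| Linear | 0 | 49.5 | 48.7 | 48.7 | 88.4 |
| | 0.5 | 62.8 | 58.0 | 26.7 | 65.8 |
| | 0.9 | 72.0 | 52.0 | 19.9 | 52.4 |
| Early plateau | 0 | 42.7 | 42.0 | 41.9 | 66.9 |
| | 0.5 | 58.6 | 52.6 | 43.4 | 41.7 |
| | 0.9 | 74.7 | 46.6 | 98.2 | 32.6 |

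On quarterly values, at r = 0, 0.5 and 0.9:

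- The corrected F rejects under the hump in 54.1%, 71.1% and 94.8%.
- For the linear difference it gives 37.0%, 48.0% and 51.3%, against 58.2%, 54.1% and 51.3% for the slope test.
- The uncorrected F rejects a true null in 5.2%, 6.1% and 10.2%.

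**5. Second set of runs.** With 155 per arm and random-slope SD 500–900 ng/mL per year (r from 500²/1000² = 0.25 to 900²/1000² = 0.81), a linear difference giving the slope test 80% power gives the corrected F 60–80% on 13 visits and 69–79% on 5. A hump of only 100 ng/mL is rejected in 10–61% of runs across all versions of the interaction test.

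**The case against.** Four points can be made for the plan.

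- **Time coding.** The text never says that visit is a factor, and speaking of regression slopes suggests continuous time. With linear continuous time the interaction would be the 1-df slope test and there would be no mismatch. This stands as far as it goes: the visit-factor reading is conventional but not stated. It does not rescue the text, because no time variable appears anywhere in the description.
- **Conclusion drawn.** Rejection "will be supportive of different trends between DFP and DFX arms". A profile test can support that, since arms 200 ng/mL apart at mid-year do have different trends. This stands: the error is relative to the stated null, not to that phrase.
- **Constructed scenario.** No section supports a symmetric 200 ng/mL hump, and both arms share the same trigger for stepping up, a ferritin rise above 20%. This stands: the hump shows what the test can do, not what is expected.
- **The remedy.** If profiles are curved, a linear-slope test cannot see purely non-linear differences, and restating the null as parallel profiles would be equally coherent. This also stands, and is why the profile test may be kept under its own label.

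A reader might infer that the interaction always costs power. The results do not support that. The loss is large under compound symmetry or with a multivariate test, 0 to 8 points for the corrected F at r of 0.5 or more, and reversed for an early plateau at r = 0.5 (52.6% against 41.7%).

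**Conclusion.** The stated null and the named test do not match on the conventional reading, and on the literal reading the model is undefined. The mismatch has three consequences, each conditional:

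- The interaction can reject with equal linear slopes: 54–95% for the corrected F under the assumed 200 ng/mL hump, against about 5% for the slope test.
- It can lose power for a linear slope difference, by an amount that depends on the covariance and the version of the test.
- Without a sphericity correction, type I error on monthly values is about 8–15% at r of 0.5 to 0.9.

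These figures assume complete data and two-sided 5%.

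A reader might go further and infer that the trial's main conclusions are at risk, or that a false slope difference will be reported. The documents do not support either. This is a supportive secondary analysis with no decision rule. The primary success-rate comparison, the sample size of 388 and the 400 ng/mL ferritin test are unaffected, and that ferritin test already gives a 95% CI for the difference in one-year change. The text should still be corrected before the data are seen, because it admits analyses that give materially different answers.

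**What to change.** In section 11.6, replace the interaction sentences with wording such as: *H0 of equal slopes will be tested by the 1-df treatment-by-time interaction, with time since baseline in months as a continuous variable, in a linear mixed model for ferritin with patient-specific random intercept and slope. The slope difference will be reported with its 95% CI.*

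If profile differences are also of interest, keep treatment by visit (categorical) as a separately labelled test of parallel profiles, with an unstructured covariance or a Greenhouse-Geisser correction. Delete the "interaction term (treatment group*monthly ferritin measure" wording.

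The cost is a text change and one re-specified model, with no new data. The downside is that the linear-slope test does not detect purely non-linear differences; the retained profile test covers those.

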2. OBJECTIVES

2.1Primary Objective

The primary objective of this study is to assess the non-inferiority of deferiprone (DFP) compared to deferasirox (DFX) in terms of changes of ferritin levels and heart iron concentration in paediatric patients affected by hereditary haemoglobinopathies requiring chronic transfusions and chelation.

2.2Secondary objectives

Secondary objectives of this study are:

- to assess treatment efficacy in terms of ferritin levels
- to assess treatment efficacy in terms of cardiac MRI T2* in patients over 10 years of age able to perform MRI scan without sedation
- to estimate the efficacy of treatments in terms of liver iron concentration (LIC) measured by MRI in all paediatric subjects able to have MRI scan without sedation
- to evaluate the safety and tolerability profile of treatments
- to assess healthcare resources utilisation and patient global assessment, including compliance and quality of life (QoL) evaluation
- to confirm the influence of demographic covariates on the pharmacokinetic disposition of treatments across the study population.

2.3Exploratory objectives

Additional and exploratory objectives of the study include the assessment of the correlation between systemic exposure to the investigational drugs and serum ferritin levels observed after one year treatment.

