4.4.2 Cardiac MRI T2*

Cardiac MRI T2* will be evaluated as secondary endpoint and will be measured in patients aged 10 years or more and able to undergo the evaluation without being sedated.

Cardiac iron load will be assessed - adopting the Cardiac MRI T2*-based technology and protocol from Resonance Health Ltd. - at baseline, and after 6 and 12 months of treatment.

Cardiac MRI T2*, as a component of the composite endpoint, will be analysed as secondary endpoint with the intent of clarifying the interpretation of the composite (Turk DC et al, 2008). Cardiac MRI T2* will be analysed as a binary variable (with success defined as in **Section 4.3.1**, criterion B). Additional details on the analysis are reported in **Section 11.2** and **Section 11.4**.

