4.4.3 Liver MRI

The efficacy of treatment in terms of LIC as measured by MRI will be a secondary endpoint and will be assessed in all patients able to undergo MRI scan without sedation.

Liver MRI will be assessed - adopting the Ferriscan® technology and protocol from Resonance Health Ltd. - at baseline and after 12 months of treatment.

Efficacy will be assessed in terms of percentage of successfully chelated patients. The criterion for success has been differently defined according to a threshold for baseline LIC. Success for patients with values of 7 mg/g dry weight or more will be defined as a reduction by 20% or more after 1 year treatment. Success for patients with a baseline less than 7 mg/g dry weight will be defined as a decrease in LIC, or if there is an increase in LIC, it will not be more than 15% after 1 year treatment despite continued transfusion with chelation therapy (**Table 2**).

Table 2. Definition of treatment success for liver MRI

Baseline LIC ≥ 7 mg/g dry weight	Reduction of 20% or more after 1 year treatment
Baseline LIC < 7 mg/g dry weight	Decrease in LIC or an increase ≤ 15% after 1 year treatment as long as the increase does not result in a LIC value > 7 mg/g dry weight

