7.3.11 Liver MRI

Liver MRI will be assessed in all patients able to undergo the MRI evaluation without sedation (regardless of their treatment assignment) at day 0 (V3)±20 days and month 12 (V15)±20 days, adopting the MRI-based FerriScan® technology from Resonance Health Ltd.

Patients will be referred to an MRI Centre for a FerriScan evaluation by the investigator. The scan data acquired will be sent to the Resonance Health central processing facility by secure transmission. A quality controlled analysis process will provide a LIC report available for download by the MRI centre.

MRI instrument specifications: the process uses patented spin density projection R2-MRI imaging technology. Each MRI screening centre will be equipped with a MRI scanner with a field strength of 1.5 Tesla.

MRI instrument calibration verification: FerriScan will be provided as a service to MRI Centres selected after assessing the suitability of their scanners for the protocol.

A Service Agreement will be established with the MRI Centres, and an Instruction Manual will be provided on all aspects of the FerriScan analysis service. A Phantom Pack will be provided by Resonance Health Ltd to complete the validation and set-up process in the MRI centres. Scan data will be transmitted for analysis at the Resonance Health quality-controlled central processing facility. Once the Phantom Pack will be successfully scanned, the MRI Centre will receive confirmation that patient scanning may commence.

[figure not shown]
Data Analysis: MRI images will be captured and securely transmitted to the Resonance Health ISO9000 and ISO13485 accredited analysis facility. The patented FerriScan analysis procedure will produce a map of liver iron and will calculate a mean LIC measurement. Results will then be available for secure download within a target time of 48 hours.

Scan data will be transmitted to the Resonance Health service centre through a secure web-based portal. Only authorised persons from MRI facilities will then be able to track its progress through the FerriScan Analysis Service Tracking system (FAST).

A LIC report will be available for download within two working days.

Evaluation procedure: the MRI evaluation process is outlined in **Figure 2**.

Figure 2. MRI evaluation procedure.

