7.3.14 Cardiac MRI T2*

Cardiac MRI T2* will be assessed in patients above 10 years of age able to undergo the MRI evaluation without sedation (regardless of their treatment assignment) at day 0 (V3) \pm 20 days, at month 6 (V9) \pm 20 days and at month 12 (V15) \pm 20 days.

The Cardiac T2* imaging protocol and the analysis are provided at Resonance Health's central image analysis facility under its quality controlled environment.

Patients will be referred to an MRI Centre to acquire cardiac T2* images. The scan data acquired will be sent to the Resonance Health central processing facility by secure transmission. A quality controlled analysis process will provide a result report available for download by the MRI centre.

MRI instrument specifications: the MRI scanner with field strength of 1.5 Tesla will be equipped with a cardiac MRI package that includes:

- RF coil suitable for acquiring cardiac images
- ECG facility
- Single breath-hold, multi-echo T2* sequence with:
Total of 8 echo times

Minimum TE between 2 and 3 ms

Maximum TE between 16 and 23 ms

MRI instrument calibration verification: cardiac T2* image analysis will be provided as a service to MRI Centres selected after assessing the suitability of their scanner. Centres not equipped with a scanner or equipped with an unsuitable instrumentation will be referred to another equipped Centre.

A Service Agreement will be established with the MRI Centres, and an Instruction Manual will be provided on all aspects of the service.

Data Analysis: MRI images will be captured and securely transmitted to the Resonance Health ISO9000 and ISO13485 accredited analysis facility. Results will then be available for secure download within a target time of 48 hours.

Scan data will be transmitted to the service centre through a secure web-based portal. Only authorised persons from MRI facilities will then be able to track its progress through the system.

A cardiac MRI T2* report will be available for download within two working days

Evaluation procedure: the MRI evaluation process is outlined in Figure 2.

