11.2 Study population

Intent to treat population

For the intent to treat (ITT) analysis all patients that have been randomized and start therapy will be included.

Per protocol population

Patients in the per protocol (PP) population for the primary efficacy analysis (PP1) are those that have received the study drugs and for whom the composite endpoint is available at baseline and after 1 year treatment, without major protocol violations.

For the secondary efficacy evaluation assessed as non-inferiority of DFP to DFX in terms of serum ferritin levels the PP population (PP2) includes only patients for whom the measure of serum ferritin is available at baseline and after 1 year treatment.

For the secondary efficacy evaluation assessed as non-inferiority of DPF to DFX in terms of successfully chelated patients according to cardiac MRI T2* the PP population (PP3) includes only patients for whom the measure cardiac MRI T2* is available at baseline and after 1 year treatment.

Safety population

The population for the safety and tolerability analysis will include all patients having received at least one dose of study medication.

PK and PKPD population

The population for the pharmacokinetic and subsequent exploratory analyses (e.g. correlation between systemic exposure and ferritin levels) will include patients who have received the investigational drugs throughout the duration of the study (i.e., 1 year) and have had a blood sample collected for the assessment of drug concentrations in plasma.

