Considering the target population of the study, it is likely that patients undergoing cardiac MRI T2* will be also those patients able to perform R2 scan for LIC assessment. LIC measures are hence expected to be available in a subgroup of the experimental population. As a consequence LIC estimates as additional secondary measure of efficacy will be analysed only in terms of descriptive statistics. Descriptive measures will be listed by visit and treatment and characterised by frequency and percentage or mean, standard deviation, median, and quartiles. The population for this analysis is the PP3.

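### Liver iron is analysed in a set defined by cardiac T2*, so every child under 10 with paired liver scans is left out, although the objective sets no age limit

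*Combined protocol and SAP*

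**What the plan says.** **Who should contribute LIC.** The secondary objective in Section 2.2 concerns LIC "measured by MRI in all paediatric subjects able to have MRI scan without sedation". Section 4.4.3 says the endpoint "will be assessed in all patients able to undergo MRI scan without sedation", and the procedure in Section 7.3.11 agrees: "Liver MRI will be assessed in all patients able to undergo the MRI evaluation without sedation". The scans are at baseline and month 12. None of these places, nor the study outline in Section 7.1, sets an age limit.

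**Who has cardiac T2\*.** Section 4.4.2 says it "will be measured in patients aged 10 years or more and able to undergo the evaluation without being sedated". Section 7.3.14 says "Cardiac MRI T2* will be assessed in patients above 10 years of age able to undergo the MRI evaluation without sedation". The two differ slightly at exactly 10 years, but neither schedules the scan below 10.

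**Which set is used for LIC.** Section 11.2 says PP3 "includes only patients for whom the measure cardiac MRI T2* is available at baseline and after 1 year treatment". The liver paragraph of Section 11.6 then states "The population for this analysis is the PP3", the same sentence that closes the cardiac paragraph. The reason offered is that "it is likely that patients undergoing cardiac MRI T2* will be also those patients able to perform R2 scan for LIC assessment". LIC is to be described without formal testing.

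**The concern.** The LIC analysis is restricted by a measurement that is not LIC and that has an age limit LIC does not have. Children under 10 would be scanned twice for LIC under Section 7.3.11, yet none of them could enter the set in which LIC is analysed.

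The stated secondary objective would then be answered only for patients of about 10 and above. The omission falls on the children for whom LIC matters most within this plan. Section 4 says iron becomes evident in the heart later than in the liver, and Section 11.6 calls cardiac MRI usually uninformative below 10. LIC is therefore the only organ-iron measure planned for these children. Section 20 also acknowledges distress and travel from MRI, a burden that is harder to justify if the specified analysis does not use the result.

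**Working it through.** The plan gives no figure for this point, so the check is mainly one of definitions, followed by a range for the number of patients.

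**Step 1: eligibility side by side**

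| | Liver MRI | Cardiac T2\* |
|---|---|---|
| Age limit | none (2.2, 4.4.3, 7.1, 7.3.11) | from 10 years (4.4.2, 7.1, 7.3.14) |
| Sedation | only if not needed | only if not needed |
| Times | baseline, month 12 | baseline, months 6 and 12 |
| Endpoint-specific set in 11.2 | none | PP3 |

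**Step 2: apply the PP3 rule.** A child under 10 at baseline has no scheduled baseline T2\*, so the pair that PP3 requires cannot exist. This remains true if the child turns 10 during the year. The exclusion is therefore 100% of under-10s, by rule and not by estimate. Two further effects follow. A patient of 10 or older with paired LIC but T2\* missing at either time is also out. And PP3 does not require LIC, so it can contain patients with no LIC to summarise.

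**Step 3: test the plan's reason.** Let C be the patients with paired T2\* and L those with paired LIC. The reason in Section 11.6 says that members of C will probably be in L. To analyse LIC in C without loss, the reverse is needed: that members of L are in C. The age rule contradicts the reverse.

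**Step 4: effect on the age subgroups.** Section 11.3 plans summaries for 1 month–5 years, 6–11 years and 12–<18 years. With PP3, the first band has no LIC data and the second draws only on patients aged 10 or 11.

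**Step 5: size.** The base is the 310 evaluable patients of Section 11.12. That figure is sound: (1.96 + 0.84)² × (0.65 × 0.35 + 0.675 × 0.325) / (0.125 + 0.025)² gives 156 per arm, or 312 in total against 310 stated, and 310 / (1 − 0.20) gives 388 as stated.

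The number of under-10s with paired LIC is 310 × u × s, where u is the share under 10 and s the share of those who can be scanned unsedated. The documents give neither; Section 6.6 fixes no numbers by age group. Both are assumptions:

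- u = 0.30, s = 0.33: 310 × 0.30 × 0.33 = 31
- u = 0.50, s = 0.50: 310 × 0.50 × 0.50 = 78
- widest low: u = 0.10, s = 0.25: 310 × 0.10 × 0.25 = 8
- widest high: u = 0.50, s = 1: 310 × 0.50 × 1 = 155

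The plan's own figures give a ceiling in one scenario. Section 11.12 regards T2\* in about 60–70% of evaluable patients as enough for a cardiac test. That is 310 × 0.60 = 186 to 310 × 0.70 = 217 patients, leaving 310 − 217 = 93 to 310 − 186 = 124 outside PP3 at any age. Only those with paired LIC would be recovered.

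**The case against.** **LIC is a descriptive secondary measure.** This stands. No test, margin, error rate or sample size depends on it, and the primary conclusion does not move. It limits the importance of the point but does not remove it, because a descriptive analysis should still cover the population named in its objective.

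**Few under-10s will be scanned.** Section 11.1 links cardiac MRI below 10 to the need for sedation, and Section 6.6 stratifies at 10 because the ability to undergo the cardiac scan differs. On that view little is lost. This stands as a limit on the number. But the protocol treats age and sedation as separate conditions: Section 4.3 has its own rule for patients of 10 or older who need sedation, and the liver scan depends on sedation alone. If no under-10 can be scanned, the correction changes nothing for them; if some can, it is needed.

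**The count is assumed.** This stands. The range 8 to 155 is too wide to serve as an estimate. In addition, a 50% share under 10 does not fit the 60–70% T2\* availability: at 60%, at most 40% can be under 10, and with half scannable the top is 310 × 0.40 × 0.50 = 62 and not 78.

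**The other LIC data are not said to be discarded.** Section 11.3 promises summaries of efficacy measurements by age, and Section 11.9 uses MRI in the exposure–response analysis. It is fair to say only that these children fall outside the specified LIC population. But Section 11.3 is generic and names no LIC set, Section 11.9 does not say whether liver MRI is meant, and Section 11.6 is explicit.

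**A later analysis plan could settle it.** Sections 11.7 and 11.12 mention one. It would have to change a stated rule, not merely fill in detail.

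**Conclusion.** The concern holds: the LIC population is wrong as written. All under-10s with paired LIC are excluded, and this rests only on the plan's own definitions. Patients of 10 or older with paired LIC but incomplete T2\* are lost as well. The number of children is unknown: 31 to 78 of 310 on the middle assumptions, 8 to 155 on the widest, and, if T2\* reaches 60–70% availability, no more than 93 to 124 patients of all ages. The consequence is confined to a descriptive secondary objective, so this should be corrected but does not threaten the trial's main result. Since ferritin and T2\* each have their own set (PP2 and PP3) and LIC has none, an oversight is the likely explanation.

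**What to change.** In Section 11.2, add an LIC set alongside PP2 and PP3: patients with LIC by liver MRI at baseline and at month 12, whatever their age and whether or not cardiac T2\* is available. In the liver paragraph of Section 11.6, replace PP3 with this set for both the success percentages and the absolute values. Report the number with paired LIC in each arm, overall and for under 10 versus 10 and older (the randomisation strata in Section 6.6), alongside the age bands already planned in Section 11.3. The under-10 split is a presentational choice; the new set is the essential part.

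The cost is a change of wording, to be made before database lock. It needs no new scans, visits or patients and leaves the sample size and the primary analysis as they are.
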